8.3. Safety Assessments

Planned time points for all safety assessments are provided in the [SoA](#). Unscheduled safety measurements may be obtained at any time during the study to assess any perceived safety issues.

8.3.1. Physical Examinations

Physical examinations will be conducted at Screening and on Day 1, Days 42, 84, and EOT. At the Follow-up visit, physical examinations will only be performed in participants with abnormalities observed at the EOT visit. Physical exams should also be performed throughout the study when clinically indicated as determined by the investigator.

A complete physical examination will include, at a minimum, assessments of the cardiovascular, respiratory, gastrointestinal, and neurological systems. Height and weight will also be measured and recorded.

Investigators should pay special attention to clinical signs related to previous serious illnesses.

Physical examination findings collected during the study will be considered source data and will not be required to be reported, unless otherwise noted. Any untoward physical examination findings that are identified during the active collection period and meet the definition of an AE or SAE ([Appendix 3, Section 10.3](#)) must be reported according to the processes in [Sections 8.4.1 to 8.4.3](#).

8.3.2. Vital Signs

Assessments comprising blood pressure (SBP and DBP; mmHg), PR(bpm), RR(times per minute) and axillary, ear, or forehead BT(C°) will be made at Screening and visits as specified in [SoA](#). If participants discontinue from study intervention prior to Day 7, Day 7 and Day 14 assessments on vital signs are not required. At the Follow-up visit, vital signs assessments will be performed only in participants with abnormalities observed at the previous visit.

On Day 1, vital signs will be measured within 1 hour before and 1 hour after the end of each dose of study intervention administration. From Day 7 onwards, vital signs will be measured once prior to study intervention administration.

Any untoward vital sign findings that are identified during the active collection period and meet the definition of an AE or SAE ([Appendix 3, Section 10.3](#)) must be reported according to the processes in [Sections 8.4.1 to 8.4.3](#).

8.3.2.1. Blood Pressure and Pulse Rate

BP and PR measurements will be assessed with a completely automated device. Manual techniques will be used only if an automated device is not available.

BP and PR measurements should be preceded by at least 5 minutes of rest with the participant in a semisupine or sitting position, in a quiet setting without distractions.

Vital signs will be taken before blood collection for laboratory tests and consist of a single measurement of PR and 3 BP measurements (3 consecutive BP readings will be recorded at intervals of at least 1 minute apart). The average of the 3 BP readings will be recorded on the CRF.

8.3.2.2. Temperature and Respiratory Rate

Temperature and respiratory rate findings collected during the study will be considered source data and will not be required to be reported, unless otherwise noted.

8.3.3. Electrocardiograms

Twelve-lead ECG recordings will be obtained at Screening and will also be performed on Day 1, Days 14, 42, 84 and EOT, while the participant remains on study intervention. All participants will have an ECG at EOT.

Standard 12-lead ECGs should be collected on visits specified in the [SoA](#) using an ECG machine that automatically calculates the HR and measures PR, QT, QTc intervals and QRS complex. Each ECG recording is to be signed and dated by the investigator or his designee. Abnormalities, if not related to the underlying disease, must either be confirmed as clinically not significant or are to be repeated until they have returned to baseline levels. Abnormalities should not be reported as AEs on the AE page of the eCRF unless they result in a clinically relevant condition.

All scheduled ECGs should be performed after the participant has rested quietly for at least 10 minutes in a supine position.

If a) a post-dose corrected QT (QTc) interval remains ≥ 30 msec from the baseline **and** is >450 msec; or b) an absolute QTc value is ≥ 500 msec for any scheduled ECG for greater than 4 hours (or sooner, at the discretion of the investigator), or c) QTc intervals get progressively longer, the participant should undergo continuous ECG monitoring. A cardiologist should be consulted if QTc intervals do not return to less than the criteria listed above after 8 hours of monitoring (or sooner, at the discretion of the investigator).

In some cases, it may be appropriate to repeat abnormal ECGs to rule out improper lead placement as contributing to the ECG abnormality. It is important that leads be placed in the same positions each time in order to achieve precise ECG recordings. If a machine-read QTc value is prolonged, as defined above, repeat measurements may not be necessary if a qualified medical provider's interpretation determines that the QTc values are in the acceptable range.

ECG values of potential clinical concern are listed in [Appendix 7, Section 10.7](#).

8.3.4. Clinical Safety Laboratory Assessments

See [Appendix 2, Section 10.2](#) for the list of clinical safety laboratory tests to be performed and the [SoA](#) for timing and frequency. All protocol-required laboratory assessments, as defined in [Appendix 2, Section 10.2](#), must be conducted in accordance with the laboratory manual and the [SoA](#). Unscheduled clinical laboratory measurements may be obtained at any time during the study to assess any perceived safety issues.

The investigator must review the laboratory report, document this review, and record any clinically significant changes occurring during the study in the AE section of the CRF. Clinically significant abnormal laboratory test findings are those that are not associated with the underlying disease, unless judged by the investigator to be more severe than expected for the participant's condition.

All laboratory tests with values considered clinically significant and abnormal during participation in the study or within 4 weeks after the last dose of study intervention should be repeated until the values return to normal or baseline or are no longer considered clinically significant by the investigator or study medical monitor.

If such values do not return to normal/baseline within a period of time judged reasonable by the investigator, the etiology should be identified and the sponsor notified.

See [Appendix 5, Section 10.5](#) for suggested actions and follow-up assessments in the event of potential DILI.

See [Appendix 6, Section 10.6](#) for instructions for laboratory testing to monitor kidney function and reporting laboratory test abnormalities.

8.3.5. Eye Examination

An eye examination will be conducted at Screening and EOT. If the participant is continuing on study intervention, an eye examination will also be performed on Day 14, 28, and 42 (also on visits as specified in [SoA](#) for participants with IM). An eye examination will be performed at the Follow-Up Visit only if abnormal at EOT. The examination will consist of visual acuity, confrontational visual field testing, and color perception testing. A qualified ophthalmologist will assess participants at Screening and through the study. Any abnormalities noted will be recorded in the eCRF.

8.3.6. Pregnancy Testing

A serum pregnancy test is required at screening. Following screening, pregnancy tests may be urine or serum tests, and must have a sensitivity of at least 25 mIU/mL. Pregnancy tests will be performed in WOCBP at the times listed in the [SoA](#). Following a negative pregnancy test result at screening, appropriate contraception must be commenced and a second negative pregnancy test result will be required at the baseline visit prior to the participant's receiving the study intervention. Pregnancy tests will also be done whenever 1 menstrual cycle is missed during the active treatment period (or when potential pregnancy is otherwise suspected) and at the end of the study. Pregnancy tests may also be repeated if requested by IRBs/ECs or if required by local regulations. If a urine test cannot be confirmed as negative (eg, an ambiguous result), a serum pregnancy test is required. In such cases, the participant must be excluded if the serum pregnancy result is positive.

8.3.7. Other Assessment

8.3.7.1. Anti-infective History

Anti-infective history of all fungal (excluding IFD under study), viral, and bacterial infections within 4 weeks prior to first dose of study intervention will be recorded in the appropriate section of the eCRF.

8.3.7.2. Non-Medication Procedures

All non-medication procedures (eg, radiation therapy), including all treatment for IFD (eg, surgery), associated with the participant's underlying disease received 2 weeks prior to the first administration of study intervention, during the study, and including the 4 weeks posttreatment period will be recorded in the appropriate section of the eCRF.

8.3.7.3. Hospitalization Status

Reason for hospitalization, date of admission, and date of discharge and will be recorded in the eCRF from screening up through the 4 weeks posttreatment period.

8.4. Adverse Events, Serious Adverse Events, and Other Safety Reporting

The definitions of an AE and an SAE can be found in [Appendix 3, Section 10.3](#).

AEs may arise from symptoms or other complaints reported to the investigator by the participant (or, when appropriate, by a caregiver, surrogate, or the participant's legally

authorized representative), or they may arise from clinical findings of the investigator or other healthcare providers (clinical signs, test results, etc.).

The investigator and any qualified designees are responsible for detecting, documenting, and recording events that meet the definition of an AE or SAE and remain responsible to pursue and obtain adequate information both to determine the outcome and to assess whether the event meets the criteria for classification as an SAE or caused the participant to discontinue the study intervention (see [Section 7.1](#)).

During the active collection period as described in [Section 8.4.1](#), each participant or legally authorized representative will be questioned about the occurrence of AEs in a nonleading manner.

In addition, the investigator may be requested by Pfizer Safety to obtain specific follow-up information in an expedited fashion.

Note: **Death** is considered an outcome of an AE. Whenever possible the underlying cause of death should be reported as the AE

8.4.1. Time Period and Frequency for Collecting AE and SAE Information

The time period for actively eliciting and collecting AEs and SAEs (“active collection period”) for each participant begins from the time the participant provides informed consent, which is obtained before undergoing any study-related procedure and/or receiving study intervention, through and including a minimum of 28 calendar days, except as indicated below, after the last administration of the study intervention.

Follow-up by the investigator continues throughout the active collection period and until the AE or SAE or its sequelae resolve or stabilize at a level acceptable to the investigator.

When a clinically important AE remains ongoing at the end of the active collection period, follow-up by the investigator continues until the AE or SAE or its sequelae resolve or stabilize at a level acceptable to the investigator and Pfizer concurs with that assessment.

For participants who are screen failures, the active collection period ends when screen failure status is determined.

If the participant withdraws from the study and also withdraws consent for the collection of future information, the active collection period ends when consent is withdrawn.

If a participant permanently discontinues or temporarily discontinues study intervention because of an AE or SAE, the AE or SAE must be recorded on the CRF and the SAE reported using the CT SAE Report Form.

Investigators are not obligated to actively seek information on AEs or SAEs after the participant has concluded study participation. However, if the investigator learns of any SAE, including a death, at any time after a participant has completed the study, and they consider

the event to be reasonably related to the study intervention, the investigator must promptly report the SAE to Pfizer using the CT SAE Report Form.

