Radiology assessment (CT/HRCT/MRI)	X ^s		X ^o			X ^l	X ^l	X	X	X	
Bronchoscopic assessment ^l	X ^l		X ^o			X ^l	X ^l	X ^l	X ^l	X ^l	
Mycological assessment (Microbiology/Histopathology/Cytopathology/Tissue Nucleic Acid)	X			X ^l				X	X	X	
Neutropenic status/ANC	X		X Ongoing-----								→
Survival status ^k			X Ongoing-----								→

- Day related to start of study treatment (Day 1), Day -1 can be the same calendar day as Day 1.
- Anti-infective history taken within 4 weeks prior to the first dose of study intervention will be collected in the eCRF.
- All medication (except for anti-infective agents, T-cell & B-cell immunosuppressants and corticosteroids) given within 2 weeks prior to the first dose of study intervention will be collected in eCRF. T-cell & B-cell immunosuppressants given within 3 months prior to the first dose of study intervention, anti-infective agents and corticosteroids given within 4 weeks prior to the first dose of study intervention will be collected in eCRF.
- A serum β-hCG testing should be performed at screening for all WOCBP according to [Section 8.3.6](#). A negative serum or urine β-hCG test must be obtained before the first dose of study intervention.
- Samples/assessments obtained within 72 hours prior to the first dose of study intervention could be accepted as the Day 1 results.
- Study intervention administration will occur every day from Day 1 to Day 84 (Day 180 for IM) or EOT.
- Adverse events will be recorded from the sign-off of informed consent to at least 28 days after last dose of study intervention.
- Only in participants with abnormalities observed at EOT.
- On Day 1, vital signs will be measured within 1 hour before and 1 hour after the end of each study intervention administration.

Period	Screening	Study Treatment									Follow-Up
Visit Identifier	Screening D-7 to D-1	Day 1	Day 2 ^p	Day 3 ^p	Day 7 ^p	Day 14 ^p	Day 28 ^p	Day 42 ^k	Day 84 ^{k,q} /Every 42 days after Day 84 ^q	End of Treatment (EOT) ^{k,m} or Discontinuation	Post Treatment Follow-up ^k (4 weeks after EOT)
Visit Window (Day) ^a					±2	±3	±3	±7	±7	±3	±7

- j. Measuring once prior to study intervention administration.

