- k. EOT, Day 42, Day 84 and Follow-up assessments are required for all participants. Participants with a successful overall response are required to return for all these visits. Participants withdrawn from study intervention or with an unsuccessful overall response prior to Day 42 are required to return to conduct a clinic visit for the EOT visit but will not be asked to return for the Day 42 or Day 84 visits; however, the participant will be contacted by telephone to obtain survival status at these time points. For participants with IM, survival status on Day 126, Day 168 and Day 180 should be collected. A Follow-up visit will be performed 4 weeks (± 7d) after last dose of isavuconazole administration.
- l. If clinically indicated.
- m. If EOT occurs within 1 week of a scheduled visit, the visits and assessment can be combined; however, the schedule of assessments for EOT must be applied.
- n. 12-lead ECG is performed 15 minutes prior to the end of the first daily infusion or approximately 3 hours post oral dose during the treatment period.
- o. If the assessments are performed at screening, the additional assessments between Day 1 and Day 7 are not required.
- p. Applicable for participants continuing on study intervention.
- q. For participants with IA or other filamentous fungi infection other than IM, if study treatment needs to be extended to longer than 84 days, sponsor should be notified. For participants with IM, procedures on Day 84, Day 126 and Day 168 should follow requirements of Day 42, maximum of study treatment is 180 days or until EOT visit.
- r. GM antigen will be tested at screening. If clinically indicated, it can be tested during Day 1 to Day 7 for participants with IA only. Any 1 of the following: 1) A single serum or plasma value ≥ 1.0 ; 2) BAL fluid ≥ 1.0 ; 3) single serum or plasma: ≥ 0.7 and BAL fluid ≥ 0.8 ; 4) two consecutive values of either serum, plasma or BAL fluid between ≥ 0.5 to <1.0 (from two separate specimens of the same category) is considered a positive result. GM meeting the protocol defined requirements within 7 days prior to first dose of study drug are eligible for enrollment.
- s. Radiology imaging obtained within 1 week (if available) prior to screening could be used.
- t. Samples/assessments obtained within 72 hours prior to screening could be used.

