4. STUDY DESIGN

4.1. Overall Design

This is a single arm, prospective, multi-center study in Chinese patients with proven, probable, or possible IFD caused by *Aspergillus* species or other filamentous fungi.

Approximately 70 participants are planned to be enrolled (assigned to study intervention) in China and approximately 66 participants are expected to be treated. The enrollment will be competitive.

Note: “Enrolled” means a participant’s, or their legally authorized representative’s, agreement to participate in a clinical study following completion of the informed consent process and assignment to study intervention. A participant will be considered enrolled if the informed consent is not withdrawn prior to participating in any study activity. Potential participants who are screened for the purpose of determining eligibility for the study, but do not participate in the study, are not considered enrolled.

All the participants will receive isavuconazole treatment. All participants receiving study medication will have the visits performed as scheduled. The longest treatment duration in this study is 84 days (maximum 180 days for participants with IM), and the total study duration for 1 participant is around 4 months (~7 months for participants with IM). For all participants, the Follow-up visit will take place 4 weeks (± 7 days) after the last administration of the study medication, and may occur before or after Day 42 and/or Day 84 (or Day 180 for participants with IM). Participants who need further antifungal treatment at the time of protocol defined longest treatment duration of isavuconazole may be switched to appropriate treatment at treating physician’s discretion.

The study will consist of 3 periods: Screening Period (up to 7 days), Treatment Period (maximum 84 days for IA or other filamentous fungi infection, or up to 180 days for participants with IM) and Follow-up Period (4 weeks after last dose of study intervention). Following the last dose of study intervention, participants who discontinued from the study intervention and participants who completed the treatment period will enter into a 4-week follow-up period for safety monitoring.

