4.4. End of Study Definition

The end of the study is defined as the date of the last scheduled procedure shown in the [SoA](#) for the last participant in the trial.

A participant is considered to have completed the study if they have completed all periods of the study, including the last scheduled visit shown in the [SoA](#).

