3. ENDPOINTS AND BASELINE VARIABLES: DEFINITIONS AND CONVENTIONS

3.1. Primary Endpoint(s)

The primary endpoint is the incidence rates of TEAEs by SOC and PT. A TEAE is defined as any adverse event (AE) that starts on or after the first administration of study intervention until 28 days after last dose of study intervention.

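### The Follow-up visit may be held from day 21 after the last dose, but the primary TEAE window runs to day 28, and no later AE contact is scheduled when the visit is early

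*Protocol*

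**What the plan says.** **Endpoint window.** SAP 3.1 defines a TEAE as an event that "starts on or after the first administration of study intervention until 28 days after last dose of study intervention". Protocol 9.3.2 gives the same window.

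**Collection period.** Protocol 8.4.1 requires AEs and SAEs to be actively elicited from consent "through and including a minimum of 28 calendar days" after the last administration. SoA footnote g agrees: "Adverse events will be recorded from the sign-off of informed consent to at least 28 days after last dose of study intervention". Section 8.4 adds that participants will be questioned about AEs during this period.

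**Last visit.** Protocol 4.1 states: "For all participants, the Follow-up visit will take place 4 weeks (± 7 days) after the last administration of the study medication". SoA footnote k repeats it: "A Follow-up visit will be performed 4 weeks (± 7d) after last dose of isavuconazole administration". The same ± 7 days stands in the Synopsis, Protocol 6.1.1 and SAP 2.3.

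**End of participation.** Protocol 4.4 states: "A participant is considered to have completed the study if they have completed all periods of the study", and goes on to include the last visit scheduled in the SoA. Section 8.4.1 then says: "Investigators are not obligated to actively seek information on AEs or SAEs after the participant has concluded study participation".

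**Length of the Follow-up Period.** Protocol 4.1 and SAP 2.3 give 4 weeks. The Synopsis, under Study Arms and Duration, gives 4 weeks ± 7 days.

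**The concern.** The visit window works against the collection rule. A site that holds the Follow-up visit on day 21 has met the SoA, yet one week of the primary endpoint's window is still open and the SoA gives no further occasion to ask about it. An event that starts in that week and is not volunteered is not recorded.

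The analysis would not reveal this. SAP 6.1 divides participants with a TEAE by the whole safety population, and SAP Appendix 3 takes the nominal Follow-up visit without a window. A week that nobody asked about is therefore treated as event-free. Characterizing TEAEs is the study's primary objective, so the error, where it occurs, lowers the primary result. SAEs and concomitant medications in that week are exposed to the same gap.

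**Working it through.** **The plan's own figure.** Protocol 9.5 gives an 86.6% probability of seeing at least one participant with an AE of 3% incidence among 66 treated: 1 − 0.97^66 = 0.8661. It reproduces.

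**The dates.** Earliest Follow-up visit: 28 − 7 = day 21 after the last dose. Latest: 28 + 7 = day 35. The TEAE window closes on day 28. Largest gap: 28 − 21 = 7 days.

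**Who is affected.** Let L be the study day of the last dose in a participant without IM. Participants with a successful response also return for the Day 84 visit (SoA footnote k; Protocol 6.1.1), itself ± 7 days. With the Follow-up visit at its earliest:

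gap = max(0, (L + 28) − max(L + 21, day of the Day 84 contact))

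| Last dose | Window closes | Gap, Day 84 contact on Day 84 | Gap, Day 84 contact on Day 77 |
|---|---|---|---|
| Day 49 | Day 77 | 0 | 0 |
| Day 50 | Day 78 | 0 | 1 |
| Day 56 | Day 84 | 0 | 7 |
| Day 57 | Day 85 | 1 | 7 |
| Day 63 | Day 91 | 7 | 7 |
| Day 84 | Day 112 | 7 | 7 |

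For a last dose on Day 84, the earliest Follow-up visit is Day 105, against a close on Day 112. For IM with a last dose on Day 180, it is Day 201 against Day 208.

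The zeros do not apply to participants withdrawn from study drug or unsuccessful before Day 42. Footnote k has them telephoned at Day 42 and Day 84 for survival status only, so those calls do not clearly cover AEs.

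**Effect on the endpoint.** Assumptions: visit dates uniform from day 21 to day 35; AE risk spread evenly from first dose to 28 days after last dose; no AE after an early visit is captured. Half of the visits then precede day 28, with a mean shortfall of 3.5 days, so the mean loss is 0.5 × 3.5 = 1.75 days.

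For a last dose on Day 84 the window is 84 + 28 = 112 days:

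- Uniform visits: 1.75/112 = 1.6%. Observed incidence 0.03 × (1 − 0.0156) = 2.95%. Detection probability 1 − (1 − 0.02953)^66 = 0.8617.
- Everyone seen on day 21: 7/112 = 6.25%. Observed incidence 2.81%. Detection probability 0.8478.

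The same calculation if all 66 had the last dose shown:

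| Last dose | Window (days) | Detection, uniform visits | Detection, all on day 21 |
|---|---|---|---|
| Day 57 (Day 84 contact on Day 77) | 85 | 0.8603 | 0.8416 |
| Day 84 | 112 | 0.8617 | 0.8478 |
| Day 180 (IM) | 208 | 0.8637 | 0.8565 |

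For an early failure the week is a larger share of that participant's own window: with a last dose on Day 28, at most 7/56 = 12.5%.

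**The case against.** **The duty already exists.** The strongest reply is that the 28-day duty is stated and does not depend on a visit. Sections 8.4 and 8.4.1 require active questioning through day 28, the SoA marks AE monitoring as ongoing, and Protocol 6.9 and 8.3.7.3 collect concomitant medications and hospitalizations through the 4-week post-treatment period. A site that stops at day 21 breaches these rules. This stands: the collection period is not too short on paper. What is missing is a scheduled contact that carries it out, and the permitted visit window invites a stop a week early.

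**Later visits fill the gap.** Many participants who stop early with a successful response come back at Day 42 or Day 84, after their window has closed. This also stands, and it confines the problem to the groups identified in the working. It does not help those treated longest, or the early failures.

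**A stronger reading of 4.4.** A reader might infer that Protocol 4.4 ends participation at a day-21 visit, so that 8.4.1 releases the investigator from asking further. The documents do not establish this. Section 4.4 requires all study periods to be completed, and 4.1 and SAP 2.3 make the Follow-up Period 4 weeks. On that text a participant seen on day 21 has not finished. The Synopsis puts ± 7 days on the period itself, and on that text the participant has. The passages conflict, and the end of the duty is unclear.

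**Conclusion.** The point holds as a mismatch between the visit window and the endpoint window. A compliant Follow-up visit can be the last scheduled AE contact up to 7 days before the primary TEAE window closes.

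The effect is downward and small: about 0.05 percentage points on a 3% AE and 0.4 points on the 86.6% for a last dose on Day 84. If every such participant were seen on day 21, the detection probability would fall to 84.8%. These sizes rest on the assumptions of uniform visit dates, evenly spread risk and complete loss of later events. The documents support none of the three, so the sizes illustrate scale only. The sample size is not affected.

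A reader might also divide 1.75 by the 28 off-treatment days and report that 6% of the endpoint's follow-up is lost. That base is wrong. The TEAE window includes the treatment period, and the endpoint is a proportion of participants, each counted once per SOC and PT, not a person-time rate.

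The change is worth making because it concerns the primary endpoint and costs little.

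**What to change.** Choose one:

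1. Set the Follow-up window to −0/+7 days (day 28 to 35 after the last dose) in every place where it appears: the Synopsis (Overall Design, and Study Arms and Duration), the SoA window row and footnote k, Protocol 4.1 and 6.1.1, and SAP 2.3. Changing only some of these would create a new inconsistency.
2. Keep ± 7 days and require a documented telephone contact for AEs, SAEs and concomitant medications on or after day 28 whenever the visit was held earlier.

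Under either option, give the Follow-up Period one length throughout, so that Protocol 4.4 and 8.4.1 can be read only one way.

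The cost is protocol and SAP wording, plus either a narrower visit window for sites or some calls. Under the uniform assumption that is at most about 33 calls (half of 66).
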